3.2.3 Other Self-Reported Outcomes

1. Change in self-reported pain intensity, as collected via the **PROMIS-PI 3-item Short Form**, from pre-intervention (baseline) to post-intervention (months 6 and 12). The primary timepoint is 12 months.
2. Change in self-reported anxiety, as collected via the **PROMIS-Anxiety 4-item Short Form**, from pre-intervention (baseline) to post-intervention (months 6 and 12). The primary timepoint is 12 months.
3. Change in self-reported depression, as collected via the **PROMIS-Depression 4-item Short Form**, from pre-intervention (baseline) to post-intervention (months 6 and 12). The primary timepoint is 12 months.
4. Change in self-reported pain intensity and pain interference as measured by **BPI pain intensity subscale** and **BPI pain interference subscale**, from pre-intervention (baseline) to post-intervention (months 6 and 12). The primary timepoint is 12 months.
5. Incidence of **intent to taper** opioid medication during 12 months, defined by self-report on the 6 and 12 month surveys.
6. **Discontinuation of opioid use at 12-months (exploratory outcome)**, defined as a 'No' response on the T3 survey question asking if the participant is currently taking an opioid medicine.

4. STUDY METHODS

4.1 Overall Study Design and Plan

We will conduct a multisite, randomized pragmatic trial to examine the comparative effectiveness of 2 interventions: a guideline-concordant opioid pharmacotherapy approach coupled with SDM (Arm 1) compared with a guideline-concordant opioid pharmacotherapy approach coupled with MI and CBT-CP (Arm 2). Participants will complete baseline, 6-month, and 12-month follow-up surveys, measuring self-report physical functioning and pain interference, along with other self-report measures. Additionally, participant's electronic health record (EHR) data will be extracted from the Common Data Model (CDM) from baseline to 18 months, which will be used to calculate average daily MED. The study design is presented in Figure 1, the study timeline is presented in Figure 2, and the data collected within each of the three study databases is presented in Figure 3. Section 4.4 below further describes the EHR data stored within the CDM, how the data is processed and transferred to RTI, and the rough time estimate for extracting and cleaning the EHR data.

Figure 1. Study Design

[figure not shown]
[figure not shown]
[figure not shown]

Figure 2. Study Timeline**Figure 3. Data within Each of the 3 Study Databases**

4.2 Study Population

The trial will be conducted in primary care and specialty pain clinics at 3 university health systems: UNC, Duke, and VUMC.

4.2.1. Participant Characteristics

The study population is defined by the following eligibility criteria.

Inclusion Criteria:

1. Aged 18 to 85 years
2. History of CNCP
3. Receiving moderate-dose COT for CNCP as evidenced by current or most recent prescription of an average daily MED of 20 mg or greater.
4. Receiving care at a participating clinic from a participating provider, as evidenced by at least 1 in-person visit within the past 12 months

Exclusion Criteria:

1. Opioid use is for pain directly related to an active cancer diagnosis
2. Opioid use is for maintenance treatment of an opioid use disorder (OUD)
3. Currently receiving CBT
4. Non-English speaking
5. Suicide attempt within the past 3 years or active suicidal ideation.
6. Other reason at the discretion of the investigator.

4.3 Study Arm Assignment and Randomization

Total anticipated enrollment is 608, with 304 participants in each arm. We expect to enroll about 203 participants per institution. This study will use real-time 1:1 ratio randomization to limit participant loss prior to treatment. Eligible participants will be randomized using a stratified, permuted-block design with random block sizes of 4 and 6 because this constrained randomization approach ensures balance between treatment groups within each of the 3 institutions (our only stratification factor) at the completion of each block. Consequently, throughout the trial, the intervention arms are expected to have approximately equal sample sizes both within an institution and across the study. We will not be able to blind participants or providers to intervention arm assignment because of the nature of the intervention.

4.4 Electronic Health Record (HER) Data in the CDM

4.4.1 Data Stored in the CDM

The EHR data extracted from the CDM contains the study's primary outcome (average daily opioid dose in MED), which is derived from each participant's prescription data. This data source also contains important subgroup variables including vital signs and CNCP, and substance use and mental health diagnoses. The study will also be extracting potential adverse events based on ICD-10 codes and insurance provider information. Each site will also perform a separate 'sidecar' request to pull out the total number of SDM visits per participant (based on attendance at a healthcare visit with a trained SDM provider, clinic notes and smartphrases), including the delivery mode of the visit (in-person vs. telehealth). A sidecar request is necessary for this type of data since this data is not included in the CDM.

4.4.2 Data Extraction and Transfer to RTI

To extract EHR data for INSPIRE participants, each participant's INSPIRE Subject ID needs to be mapped to their Medical Record Number (MRN). To accomplish this, the RTI statistician sends an Excel Trial Table to each site coordinator that contains each participant's INSPIRE Subject ID and the date in which they either completed or withdrew from the study. The site coordinator then populates each participant's MRN in the Trial Table (note: RTI is not provided MRNs) and sends it to the site programmer. Prior to this, the site programmer is provided an INSPIRE Query Package from RTI that contains SAS programs designed to extract the appropriate EHR data from their CDM. The site programmer will run the SAS program, which calls in the Excel Trial Table and extracts all pre-specific EHR data for each INSPIRE participant. The resulting SAS datasets are uploaded to the RTI SFTP server by the site programmer after they have cross-walked the output with the expected data dictionary (for a brief QAQC check).

4.4.3 Timeline and Data Cleaning for EHR Data Extraction

Each study site's CDM is refreshed with new EHR data 4 times a year: January, April, July, and October. Additionally, there is up to a 3-month lag time when data from a participant's clinic visit is entered into some institutions' EHR research database (which feeds into the CDM). For each CDM data transfer, the initial transfer will occur immediately after the scheduled CDM data refresh. After RTI receives the initial transfer, data managers and statisticians will review the EHR data for quality checks including, but not limited to: receipt of all expected data tables per participant, missing prescription data fields, participants with an average baseline MED of < 20, out of range fields, and potential repeat/duplicate data. The RTI data manager will query the site regarding identified data quality issues. Based on the site's response regarding queries, a final cleaned extracted EHR dataset is expected approximately 2-months after the initial data extraction. Figure 4 below depicts the timing and processing for each planned EHR data extraction.

Figure 4. EHR Timeline and Processes

	2019	2020	2021	2022				2023						2024					
	Oct	Nov	Dec	Jan-Dec	Jan-Dec	Jan-Mar	Apr	May	Jun	Jul-Dec	Jan	Feb	Mar	Apr-Jun	Jul	Aug	Sep	Oct-Dec	Jan-Mar
I. EHR Data Extraction ^{1,2}																			
a. Initial Extraction																			
b. Data Review and Clean																			
c. Final Extraction (clean data)																			
II. Data Analysis																			
<small>¹ There is roughly a 3-month lag between a participant's clinic visit and when that EHR data will be available within the CDM</small>																			
<small>² The CDM is updated 4 times a year: January, April, July, and October. Each CDM data extraction above is to be scheduled after the CDM database has been updated.</small>																			

4.5 General Masking Procedures

Masking procedures are not applicable for this study since it is an unmasked behavioral intervention trial. However, interim reporting of summary statistics by intervention arm (such as reports to the DSMB), will be blinded and only accessible to the study statistician. The statistical lead, project PI, and all project staff and site PIs and staff remain blinded to cumulative data.

4.6 Database Lock

As noted above, 3 different study databases will provide data. The last participant is expected to be enrolled in March 2022 and the last intervention visit may go until March 2023. The last T2 (6-month) survey is expected in September 2022 and the last T3 (12-month survey) is expected in March 2023. The T2 and T3 survey database will be locked approximately one month after the last completion of the T3 survey. The REDCap database lock will occur after the last participant's final intervention status CRF has been completed (i.e., completed the 12-month intervention phase) and all data queries have been resolved by the study sites. As mentioned above in section 4.4.3, the EHR data extraction takes places 3 times across the study. *Although the final EHR data extraction is planned to take place in July or August 2023, or 18-months after the last participant was enrolled into the study, it will likely not contain 18-months of EHR data for the last participant since there is up to a 3-month lag between clinic visit and data inclusion in the CDM. However, all participants should contain 12-months of EHR data in the final extraction (the study's primary timepoint).* The final EHR data extraction will be considered final and locked after the sites have addressed any potential RTI queries and transferred a clean dataset (expected to occur ~2-months after the initial data transfer). The locked datasets from each of the 3 databases will be used to derive the final analysis dataset which will be used to perform the analyses described within this SAP. Analysis data specifications are further described in section 9.2.

The study is designed as intention-to-treat (ITT). If a participant discontinues further intervention or participation in the study, every attempt will be made to continue to perform the required study-related follow-up surveys and EHR data extraction. However, surveys and EHR data will not continue to be collected from those who are determined ineligible, withdrew from all study activities, investigator withdrew and other (depending on the reason).

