## 2.5 Study Duration

*Cross-reference: UNC IRBIS Application sections A.4.2, A.4.5, B.3.3*

We anticipate that in its entirety the study will last 72 months, from February 2018 to January 2024. Enrollment is expected to begin in April 2019 and will continue until enrollment has been completed, but no later than March 2022, as shown in Figure 3.

*Figure 3. Study Timeline*

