9.2 Variable Definitions

The table below provides a description of the study endpoints and subgroup categories, including data type and derivation. More information regarding these variables is provided in the analysis dataset specification file.

Variable	Type	Definition
Primary Outcome		
Change in opioid dose (based on average daily MED) from baseline to 12 months post-randomization	Continuous	
The primary outcome will be derived from EHR data from the Mid-South CDRN data warehouse. Total morphine equivalents for each prescription will be calculated by multiplying the quantity of each prescription by the strength of the prescription (milligrams of opioid per unit dispensed). The quantity-strength product is then multiplied by conversion factors to estimate the milligrams of morphine equivalent to the opioids dispensed in the prescription. The total average dose in morphine equivalents per day supplied is calculated by summing the morphine equivalents for each prescription filled during a given period and dividing by the number of days supplied. The below algorithms further describe derivation of the primary outcome measure:
 $\text{One Prescription's MED Daily (MEDD)} = \frac{(\text{Strength per unit}) \times (\text{Quantity dispensed}) \times (\text{MME Conversion factor})}{(\text{Days Supply})}$ $\text{Avg. MEDD per Timeframe} = \frac{(\text{Multiply each RX's MEDD by Days Supply}) \text{ then } (\text{Sum all RX's Total MEDD for those prescriptions within timeframe})}{\text{Total number of days in timeframe}}$ 
Opioid dose will be calculated as the prescribed milligrams of daily MED averaged over the 90 days prior to randomization and averaged over 90-days for the time periods of 3, 6-, 9-, 12-, 15- and 18-months post randomization.
 
We expect no missing prescriptions, yet some participants might not have complete data because (a) they discontinued and removed consent to use data after that date, (b) they were lost to follow-up and may have moved out of the clinic's care, (c) the last CDM transfer did not contain their data up to 18 months past baseline or (d) they discontinued taking opioids. Cases of (d) will be identified by the response to the T2 and T3 survey item G20 "Are you currently taking an opioid medicine now?". If the response indicates "no" and opioid prescriptions last dose date ends before month 18, then an MED of zero will be assumed for all days after the last dose date to Month 18 (or date participant removed informed consent, if applicable). Otherwise, if there is not a "no" response

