Change in Brief Pain Inventory (BPI) pain severity summary measure from baseline to 6- and 12-months post-randomization.	Continuous	
The BPI assess pain at its “worst”, “least”, “average”, and “now”. Although clinical trials often use pain at “worst” and “average” to represent single pain severity, the BPI’s developers recommend that all four severity items be used, because the models for validation of the BPI included all four items.
 
A composite pain severity score is derived by taking a mean severity score of the four severity questions, if all four items are answered.
 
The BPI severity score is also used to define the participant’s baseline pain severity.
 
The BPI User Guide is found at: https://www.mdanderson.org/documents/Departments-and-Divisions/Symptom-Research/BPI_UserGuide.pdf

BPI pain severity categories	Categorical	
BPI pain severity sub score categories at baseline are defined as (Boonstra 2014):
 
Mild: < 3.5
 
Moderate: 3.5 – 7.4
 
Severe: 7.5+

Change in Brief Pain Inventory (BPI) pain interference summary measure from baseline to 6- and 12-months post-randomization.	Continuous	
The BPI measures how much pain has interfered with seven daily activities: general activity, walking, work, mood, enjoyment of life, relation with others, and sleep. BPI pain interference is scored as the mean of the seven pain interference items, This mean can be derived if more than 50% (or 4 of 7) of the total items have been completed.
 
The BPI User Guide is found at: https://www.mdanderson.org/documents/Departments-and-Divisions/Symptom-Research/BPI_UserGuide.pdf

Variable	Type	Definition
Discontinuation of opioid medications (from T3 Survey) self-report	Binary	
Discontinuation of opioid medication at 12-months will be defined as a response of "No" to the G20 question on the T3 survey that asks: "Are you currently taking an opioid medicine now? Commonly prescribed opioids include hydrocodone, oxycodone, codeine, morphine, and fentanyl." If a participant responds "No" to the survey but has opioid prescriptions in the EHR within 15-days prior to the 12-month timepoint throughout the 18-month timepoint, the participant will be considered as still taking opioid prescriptions.
 
A response of "don't know" will be lumped with a response of yes, both indicate the patient has not discontinued their opioid.

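### The final EHR extraction falls 16-17 months after last enrolment, not 18, and the zero-fill rule does not stop where the extracted data end for late enrolees who report having stopped opioids

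*SAP*

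**What the plan says.** **Dates.** SAP 4.6 states: "The last participant is expected to be enrolled in March 2022". Protocol 2.5 agrees, allowing enrolment to continue "but no later than March 2022, as shown in Figure 3". SAP 4.6 adds: "The last T2 (6-month) survey is expected in September 2022 and the last T3 (12-month survey) is expected in March 2023". It then says the "final EHR data extraction is planned to take place in July or August 2023, or 18-months after the last participant was enrolled".

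**Lag.** SAP 4.4.3 says that "there is up to a 3-month lag time when data from a" clinic visit enter the research database at some institutions. SAP 4.6 accepts that the last participant will probably not have 18 months of EHR data. It gives the lag as the reason, and expects 12 months of data for everyone.

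**Days after the last prescription.** SAP 9.2 lists four reasons for incomplete dose data. Truncation by the last CDM transfer is reason (c). Stopping opioids is reason (d), identified by a no to item G20 at T2 or T3. If the answer is no and the last dose date falls before month 18, "then an MED of zero will be assumed for all days after the last dose date to Month 18", or to the date on which consent was removed. With no such answer, or no survey, days after the last dose date are missing.

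**The concern.** There are two linked faults. The 18-month label does not match the dates printed beside it, so a reader will think month 18 is reached for everyone apart from the lag, and that only the last participant falls short.

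The zero-fill rule also has no stop at the end of the extracted data. A late enrolee can fall under reasons (c) and (d) together, and the SAP does not say which takes precedence. In a truncated record the last dose date will normally fall before month 18 because the record stops there, so the prescription condition then confirms nothing about stopping.

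What is at stake is the month-15 and month-18 estimates. Month 18 is a key secondary timepoint (SAP 3.2.1), and both windows enter the primary repeated-measures model (SAP 9.3). Days that nobody has observed would be scored as zero or as missing according to one answer on an unblinded survey.

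**Working it through.** **1. The stated interval.** SAP 4.6's own convention is last enrolment March 2022, plus 6 months = September 2022 (T2), plus 12 months = March 2023 (T3). Plus 18 months is therefore September 2023.
- March 2022 to July 2023: 12 + (7 − 3) = 16 months.
- March 2022 to August 2023: 12 + (8 − 3) = 17 months.

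The stated 18 months is not reproduced. By day of the month the interval runs from 15.0 months (31 March 2022 to 1 July 2023) to 18.0 months (1 March 2022 to 31 August 2023), so 18 is reached only at that one extreme. Counting to the cleaned dataset about 2 months later would give 18-19 months, but the sentence dates the extraction itself, and the next CDM refresh after July is October (SAP 4.4.3).

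**2. Usable follow-up for the last enrolees.**
- No lag: 16-17 months. The month-15 window (months 12-15) is complete and the month-18 window (months 15-18) is partly observed.
- Full 3-month lag: 16 − 3 = 13 to 17 − 3 = 14 months (12.0 to 15.0 across day-of-month extremes). The month-15 window is partly observed and the month-18 window essentially unobserved.
- In both cases months 9-12, the primary window, are covered.

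**3. Who has a complete month-18 window.** Latest complete enrolment date = extraction date − lag − 18 months. Enrolment runs from April 2019 (Protocol 2.5) to March 2022, which is 36 months, and 526 were randomised (SAP 6). Even accrual is an assumption and gives 526/36 = 14.6 per month.

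| Lag | Extraction date | Complete if enrolled by | Later enrolment months | Participants |
|---|---|---|---|---|
| none | 1 July 2023 | 1 January 2022 | 3 | 3/36 × 526 = 44 |
| none | 31 August 2023 | 28 February 2022 | 1 | 1/36 × 526 = 15 |
| 3 months | 1 July 2023 | 1 October 2021 | 6 | 6/36 × 526 = 88 |
| 3 months | 31 August 2023 | 30 November 2021 | 4 | 4/36 × 526 = 58 |

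**4. The rule applied to one case.** Take a March 2022 enrolee whose last supply ended in February 2023 and who answers no at T3 in March 2023. Month 18 is September 2023. Under the full lag the record is complete to April or May 2023, so the last 4-5 months are unobserved and scored 0 MED. With no lag the unobserved stretch is 1-2 months. The same prescription record with no T3 survey gives missing for those days.

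**5. How many are exposed to unsupported zeros.** The documents do not say. Survey completion was tracking around 60% (SAP 6), and SAP 9.6.3 expects too few discontinuations to stratify by site. As an illustration only, assume 5-15% of completers answer no:
- Full lag: 58 × 0.6 × 0.05 = 1.7 to 88 × 0.6 × 0.15 = 7.9, about 2 to 8 people.
- No lag: 15 × 0.6 × 0.05 = 0.5 to 44 × 0.6 × 0.15 = 4.0, at most about 4 people.

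**The case against.** The strongest reply is that little turns on this. SAP 4.6 already discloses that 18-month data will be incomplete. Month 12 is covered, the only formal tests are at 12 months (SAP 7.6), and month 18 is to be described (SAP 9.1). The default for days after the last dose date is missing, handled under the missing-at-random assumption. Truncation is listed separately from discontinuation, and SAP 9.2 refers to the applicable survey, which may be meant to limit the rule. For someone who reports stopping and whose prescriptions have ended, zero may be the true value. Randomisation is blocked within institution, so late enrolment should be balanced between arms.

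Most of this stands and limits the point. Two things do not. The disclosure names the wrong extent and only one cause: the shortfall exists with no lag and reaches beyond the last participant. And the rule as written still runs past the data, because the SAP neither defines which survey is applicable nor says that reason (c) overrides reason (d).

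A reader might also want to act on the exploratory 12-month discontinuation outcome, where a no is overridden by prescriptions "within 15-days prior to the 12-month timepoint throughout the 18-month timepoint". The look-ahead is indeed shorter for late enrolees. But narrowing the override would redefine that endpoint, and nothing here requires it.

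**Conclusion.** The interval is 16-17 months on the SAP's own dates. With the full lag, the last enrolees' data are complete only to about month 13-14. The month-18 window is incomplete for about 15-44 of 526 with no lag and 58-88 with the full lag. These counts rest on even accrual, which the documents do not show (SAP 6 says enrolment was slower than planned), and on one lag applied at every site, although SAP 4.4.3 gives 3 months as a maximum at some institutions.

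The unsupported zeros are confined to late enrolees who answer no to G20. Their number is unknown and likely small. The month-15 and month-18 estimates are affected directly, and month 12 only indirectly through the shared model.

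A reader might infer that unobserved months become zeros for late enrolees in general, or that the rule overstates dose reduction or favours one arm. The documents do not support either reading. The general rule is missing. Zeros overstate reduction only if these people were still being prescribed opioids, or resumed them, after the data end. The split of no answers by arm is not given, and a difference could be a real effect.

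**What to change.** Two changes to the SAP:

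1. In 4.6, give the interval as 16-17 months, and say that the month-18 shortfall arises from the extraction date as well as the lag and affects more than the last participant.
2. In 9.2, end zero-filling at the earliest of month 18, removal of consent and the site's data-complete date (extraction date minus that site's lag). Set later days to administratively missing, whatever the G20 answer.

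The cost is SAP wording and one date per site, with no new data. Moving the final pull to the October 2023 CDM refresh is not recommended as the remedy. Under the full lag, data would be complete to about July 2023, which is 16 months for a March 2022 enrolee and still short of month 18. Cleaning would add about 2 months, close to the January 2024 study end in Protocol 2.5.

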### 3.12 Withdrawal from the Study

*Cross-reference: UNC IRBIS Application section A.7.3.*

Participants are free to withdraw from participation in the study at any time upon request. An investigator may discontinue or withdraw a participant from the study for the following reasons:

- If any adverse event (AE) or other medical condition or situation occurs such that continued participation in the study would not be in the best interest of the participant.
- Disease progression that requires discontinuation of the study intervention.
- If the participant meets an exclusion criterion (either newly developed or not previously recognized) that precludes further study participation.

The reason for participant discontinuation or withdrawal from the study will be recorded in the Enrolled Participant Database. The study will retain participant data collected prior to withdrawal. We will not contact the participant to obtain any more self-report data, and the participant will not receive any further intervention. However, if the participant has completed any part of the intervention, we would like to continue to extract the participant's EHR data, and we will use the **Withdrawal Consent Addendum** (see Appendix) to seek permission to do so. If the participant withdraws prior to participating in the intervention, we will not collect any more of their data.

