#### 5.3.1 Primary Analysis Methods for Opioid Usage Outcome

For reduction in opioid use, we will use a constrained linear mixed model to generate point and interval estimates of the reduction in opioid dose MED from baseline to **4, 6, 8, 10, 12, 14, 16, and 18** months and to test the hypothesis that this reduction differs between the 2 intervention arms. While the primary and secondary time assessments are at 6, 12 and 18 months, all available opioid prescription data from baseline through 18 months will be included in the model. This approach will provide consistent estimates and valid inferences under missing at random (MAR) data assumptions while accounting for correlation among multiple measures on the same participant. This mixed model will improve the power of the study and the precision of all estimates by allowing all available measures for an individual to be incorporated in the analysis, even if other timepoints are missing. The model will include fixed effects for the treatment group, time interval (as a categorical variable), treatment-by-time interaction, baseline opioid dose, the stratification effect of institution, and random effects for participant. An intervention-arm-specific Toeplitz correlation structure will be assumed for the within-participant measures, to reflect the changing correlation of these measures over time and permit the

correlation structure to differ between study arms. The model will be used to generate point and interval estimates and to test differences in mean changes in opioid dose between the 2 intervention groups at 12 months (primary timepoint) and to generate point and interval estimates at 6 and 18 months (secondary timepoints).

This model treats missing data as ignorably missing, assuming any missing data are missing at random, after accounting for baseline opioid dose. Sensitivity analyses based on multiple imputation procedures will be performed to evaluate departures from critical distributional and missing data assumptions. Plans to address missing data are further presented below (see *Missing Data Section*) and will be described in detail in the Statistical Analysis Plan. Assessments of model assumptions and goodness-of-fit will also be specified in the Statistical Analysis Plan.

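### SAP 4.6 stops EHR dose collection for participants found ineligible or withdrawn by the investigator, without the exposure-and-permission condition in Protocol 3.12

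*SAP*

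**What the plan says.** SAP 4.6 describes the study as intention-to-treat and promises that, after a participant discontinues, "every attempt will be made to continue to perform the required study-related follow-up surveys and EHR data extraction". The next sentence takes part of that back: "surveys and EHR data will not continue to be collected from those who are determined ineligible, withdrew from all study activities, investigator withdrew", with a tail that reads "investigator withdrew and other (depending on the reason". It mentions neither intervention received nor permission.

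Protocol 3.12 has one withdrawal rule for participant requests and investigator decisions alike: "An investigator may discontinue or withdraw a participant from the study for the following reasons". The reasons listed are an adverse event or other medical situation, disease progression, and "If the participant meets an exclusion criterion (either newly developed or not previously recognized) that precludes further study participation". What happens to EHR data then depends on exposure. On one side, "if the participant has completed any part of the intervention, we would like to continue to extract" the EHR data, with permission sought through the Withdrawal Consent Addendum. On the other, "If the participant withdraws prior to participating in the intervention, we will not collect any more of their data". No further self-report data are sought after withdrawal in either case.

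On missing data, Protocol 5.3.1 states: "Sensitivity analyses based on multiple imputation procedures will be performed to evaluate departures from critical distributional and missing data assumptions". Protocol 5.3.3 names control-based imputation and a tipping-point analysis, and attaches no condition to either. SAP 9.4 runs the attrition model only if more than 20% of 12-month MED is missing, and the tipping-point analysis only if, in addition, the primary result is significant.

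**The concern.** The 12-month MED is the primary outcome and comes passively from the EHR. For someone who has stopped the intervention but agrees to continued extraction, it can still be collected without a visit. Read plainly, SAP 4.6 discards it for two categories of randomised participant that the protocol meant to keep where permission is given.

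The loss could be informative. The investigator's reasons for withdrawal include adverse events and disease progression, and Protocol 5.3.3 accepts that attrition may be associated with opioid use. The mixed model treats the resulting gap as missing at random. Under SAP 9.4, if total missingness is 20% or less, neither the attrition model nor the tipping-point analysis runs.

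**Working it through.** **1. Where the two rules differ.**

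| Participant | SAP 4.6 | Protocol 3.12 | Conflict |
|---|---|---|---|
| Investigator-withdrawn or later ineligible, no intervention | stop EHR | stop EHR | none |
| Same, some intervention, no permission | stop | stop | none |
| Same, some intervention, permission given | stop | continue | **yes** |
| Left all study activities by choice | stop | continue only with permission | not pressed; can be read as declining the addendum |
| Other | depends on an unstated reason | depends on exposure and permission | cannot be determined |

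Stopping surveys after withdrawal is not in dispute, since Protocol 3.12 stops them too.

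**2. Is it a deliberate departure?** The SAP flags its other departures: the time intervals (9.2, 9.3), the random subject effect (9.3) and the discontinuation outcome (9.6.3). It flags none here. Its own protocol history (section 1, version 3.0) lists the addendum.

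**3. Is the SAP consistent with itself?** SAP 9.2 gives four reasons for incomplete dose data: consent removed, lost to follow-up, last transfer too early, and opioids discontinued. Extraction stopped because the investigator withdrew the participant, or because ineligibility came to light, is not among them. Nor is it in the 12% missing-data allowance of Protocol 5.3.3, which names EHR loss to follow-up and withdrawn consent.

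**4. The plan's own figures.** With difference 10, SD 40, two-sided 0.05 and 80% power, n per arm = 2 × (1.960 + 0.842)² × 40² / 10² ≈ 251.2, rounded up to 252 (504 in total, against 506 stated). 506 × 1.20 = 607.2, rounded up to 608. With 526 randomised, 526 / 1.2 ≈ 438 effective participants give 74.4% power, against 75% stated. The figures reproduce, and this point changes none of them.

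**5. Size.** The only ceiling is all-cause discontinuation as of June 2023 (SAP 6): 0.20 × 526 = 105.2, about 105 participants. The affected group is an unknown part of that.

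The following is a purely assumed one-arm scenario. Suppose a share p of one arm (526 / 2 = 263) falls in the conflict row before month 12, and their change differs by d MED from what their earlier doses predict. The arm difference then shifts by p × d.

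| p | Patients (p × 263) | Share of one arm's discontinuations, if split evenly (52.6) | Shift, d = 10 | Shift, d = 20 |
|---|---|---|---|---|
| 2% | 5.3 | 10% | 0.2 MED | 0.4 MED |
| 5% | 13.2 | 25% | 0.5 MED | 1.0 MED |
| 10% | 26.3 | 50% | 1.0 MED | 2.0 MED |

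Standard error at 12% missing: 40 × √(2 / (263 × 0.88)) = 3.72 MED. At 20% missing: 40 × √(2 / (263 × 0.80)) = 3.90 MED. The shifts run from 0.2 / 3.72 = 0.05 to 2.0 / 3.72 = 0.54 standard errors, in either direction. If both arms are affected equally, the shift is zero. The lower rows are demanding: the last needs half of one arm's discontinuations to fall in this narrow group, with no offset in the other arm.

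**The case against.** The best defence is that SAP 4.6 is a loose summary sentence in a section on database lock, while SAP 9.2 governs how the dose is derived and ties truncation to removed consent, broadly as the protocol does. The closing parenthesis might also be read as qualifying the whole list. This softens the point but does not remove it. The natural reading attaches the parenthesis to the last category only. Even the looser reading leaves extraction to an unstated judgement instead of the protocol's condition. SAP 9.2 shows that two parts of the SAP disagree; it does not say which one the sites follow.

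It is also fair that the affected group may be almost empty, that the documents do not show whether any addendum was offered or signed, and that the SAP 9.4 conditions apply to all missing MED whatever SAP 4.6 says. All of this stands and limits the weight of the point.

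A reader might infer more than the documents support:

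- That intention-to-treat is abandoned. It is not: SAP 5.1 keeps these participants in their assigned arm, and their earlier doses stay in the model.
- That the Trial Table date in SAP 4.4.2 cuts extraction off at withdrawal. That section says the date is supplied, not that it ends the query. Participation is complete after the 12-month survey (Protocol 3.11), yet doses are needed to month 18, so the date cannot be a simple cut-off for completers. This needs confirming, not assuming.
- That the primary result is biased, or its error rate inflated. Nothing gives the number, split by arm or direction.

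**Conclusion.** The inconsistency is real and confined to one group: participants withdrawn by the investigator or later found ineligible, after some intervention, who gave or would give permission. For them SAP 4.6, read plainly, stops primary-outcome data that Protocol 3.12 would keep, and no reason is recorded. Loss of data is a consequence of the wording, not something the documents show to have happened.

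The effect cannot be estimated and may be negligible. The shifts of 0.2 to 2.0 MED rest entirely on assumed values of p and d and on the loss falling in one arm. The upper end is unlikely. The change is still worth making, because the protocol already provides the route, the outcome is primary, and the planned check on the missing-data assumption has become conditional in the SAP. Confidence is high on the conflict between the texts and low on any effect on the result.

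**What to change.** 1. Amend SAP 4.6 to follow Protocol 3.12. For investigator-withdrawn or later-ineligible participants who completed any part of the intervention and have signed the addendum, continue EHR extraction to month 18. Stop it otherwise. Define the other category. Confirm with the site programmers that the query does not cut off consenting participants at their withdrawal date. If the stricter rule was intended, record it as a departure with its reason, as the SAP does elsewhere.
2. In the CONSORT reporting already planned in SAP 8.1, give by arm and reason the number whose EHR extraction was stopped, and whether they had started the intervention.
3. Run the sensitivity analysis of the missing-at-random assumption for 12-month MED whatever the primary p-value and whatever the percentage missing, as Protocol 5.3.1 and 5.3.3 plan. Vary the shift separately by arm, for example from -20 to +20 MED (an illustrative range). SAP 9.4 currently shifts only the arm with the weaker change.

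Recontacting withdrawn participants and re-running the query is not proposed. It is not shown to be needed, nor feasible so close to the final extraction planned for July or August 2023.

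The cost is some SAP wording, one check with the sites, a few more cells in a planned display and one further analysis. No visits or new consent documents are needed.
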